## **6. TREATMENT PROCEDURES**

### **6.1 Classification of Products**

The Amgen Investigational Product and/or placebo used in this study include: AMG 529 and placebo.

The Investigational Product Instruction Manual (IPIM), a document external to this protocol, contains detailed information regarding the storage, preparation, destruction, and administration of AMG 529 and placebo.

### **6.2 Investigational Product**

All investigational product will be administered at the research facility by a qualified staff member.

A physician must be available at the time of administration of Investigational Product.

#### **6.2.1 Amgen Investigational Product AMG 529 and Placebo**

AMG 529 for SC and IV administration will be manufactured and packaged by Amgen Inc. and distributed using Amgen clinical study drug distribution procedures.

AMG 529 is provided in 5 mL sterile vials filled with a 1 mL deliverable volume of 70 mg/mL AMG 529. Placebo will be presented in identical containers and stored/packaged the same as AMG 529.

##### **6.2.1.1 Dosage, Administration, and Schedule**

The planned doses of AMG 529 are shown in [Table 2](#). Doses will be administered on Day 1 following all required pre-dose procedures. All cohorts will be dosed in a staggered fashion where 2 subjects will be dosed (randomized to AMG 529 or placebo in a 1:1 ratio), followed by the remaining 6 subjects separated by at least 24 hours, provided there are no safety or tolerability concerns as assessed by the principal investigator.

**Table 2. Planned Treatment by Cohort**

Cohort	Dose/Route	No. of Subjects		Total
		AMG 529	Placebo	
1	21 mg SC	6	2	8
2	70 mg SC	6	2	8
3	210 mg SC	6	2	8
4	420 mg SC	6	2	8
5	700 mg SC	6	2	8
6	70 mg IV	6	2	8

The dosing schedule is described by a [schema](#) in the protocol synopsis.

The date, time, package lot number, and quantity administered are to be recorded on the individual subject's Investigational Product Administration CRF prior to database lock.

The effects of overdose of this product are not known.

#### **6.2.1.2 Dose-cohort Study Escalation and Stopping Rules**

##### **6.2.1.2.1 Dose Level Review Meetings**

Dose Level Review Meetings will be held to review data, monitor safety and make dose change decisions. The Dose Level Review Meeting (DLRM) members will be composed of the principal investigator or designee, the unblinded Amgen Medical Monitor, Amgen Global Safety Officer or designee, Amgen Clinical Research Study Manager or designee, and biostatistics representative or designee. Additional members may be added as needed (eg, clinical pharmacology scientist). The DLRM voting members include the principal investigator or designee, Amgen Medical Monitor and Amgen Global Safety Officer or designee.

The DLRM members are responsible for dosing decisions, which may include escalation to the next planned dose, escalation to an intermediate dose (a dose lower than the next planned dose), de-escalation to a lower dose; continuation, delay, or termination of dosing; or repetition or expansion of a cohort. Study data, including demographics, investigational product administration, medical history, concomitant medications, adverse events (including serious adverse events), electrocardiograms, vital signs, and safety laboratory results will be reviewed. If available, emerging PK and PD data may also be reviewed in a manner that does not unblind individual treatment assignments. The data to be reviewed may not have been monitored or queried.

Except for the unblinded Amgen Medical Monitor who will review data on an ongoing basis throughout the duration of study in an unblinded manner, data will be reviewed by the rest of the DLRM members in a blinded manner (ie, treatment assignment will not be revealed) unless unblinding is deemed necessary for the review team to make dosing decisions. Unblinding can be performed at any time by the investigator or Amgen if deemed necessary for subject safety. If deemed necessary, unblinding will be performed according to Amgen standard procedures.

Escalation to a higher dose cohort will only proceed when the previous dose regimen has been found to be safe and reasonably tolerated based on available study data through study day 15 for all subjects and upon unanimous decision of the DLRM members. Available data from previous cohorts will also be considered. The next cohort will be open for enrollment immediately following the DLRM decision. Enrollment can be initiated in cohort 5 and cohort 6 after the dose regimen in cohort 4 has been found to be safe and well tolerated. Cohort 6 will start enrollment after the completion of cohort 5 enrollment.

The planned dose escalation schedule may be modified based on treatment-emergent data (safety and/or PK). Dose adjustments, if any, will be made on a treatment cohort and not on an individual basis, and will be agreed upon by Amgen in coordination with the principal investigator.

The review of available safety data and dosing change decisions will be documented in meeting minutes. Amgen will issue a written notification of the dose change decision to investigators.

#### **6.2.1.2.2 Dose Stopping Rules**

Determination of the severity of adverse events will be as follows: grade 1 = mild (eg, asymptomatic or mild symptoms, clinical or diagnostic observations only, intervention not indicated, or does not interfere with activity); grade 2 = moderate (eg, minimal intervention indicated or interferes with activity); grade 3 = severe (eg, medically significant but not immediately life-threatening, prevents daily activity, or requires treatment); grade 4 = life-threatening (ie, refers to an event in which the subject was, in the view of the investigator, at risk of death at the time of the event); and grade 5 = fatal.

Dosing will be stopped or modified by the DLRM members if suspected adverse drug reactions and/or changes in safety data (including but not limited to vital signs, electrocardiogram (ECG), or clinical laboratory results) are observed and these changes

pose a significant health risk. The unblinded Amgen Medical Monitor will review data in an unblinded manner on an ongoing basis, and may suspend dosing and convene a DLRM at any time based on emerging safety data. In addition, dose escalation will be stopped or modified as shown in [Table 3](#).

Clinically or medically significant suspected adverse drug reactions, and serious adverse events considered to be related to study procedures will be followed until resolved or considered stable.

**Table 3. Cohort Dose Stopping Rules**

Scenario	Action
Any occurrence of a Grade 2 suspected adverse drug reaction in 2 or more subjects in the same cohort	

• Stop dosing additional subjects and convene DLRM (if event occurs outside of the regularly scheduled DLRM)

• Review adverse event and all relevant safety data for evidence of relationship to treatment and clinical or medical significance

• Consider unblinding as appropriate

• Upon unanimous decision by the DLRM members, one of the following decisions may be made:

○ stop enrollment of the cohort (if applicable)

○ resume enrollment of the cohort as planned

○ resume enrollment of the cohort at a lower dose

○ expand the cohort at the same dose

○ add a lower dose cohort to the study

○ escalate to an intermediate dose (a dose lower than the next planned dose)

○ escalate to the next planned dose

Page 1 of 2

Footnotes defined on next page of the table

**Table 3. Cohort Dose Stopping Rules**

Scenario	Action
Any occurrence of a Grade 3 or greater suspected adverse drug reaction	
 
• Stop dosing additional subjects and convene DLRM (if event occurs outside of the regularly scheduled DLRM)
 
• Review adverse event and all relevant safety data for evidence of relationship to treatment and clinical or medical significance
 
• Consider unblinding as appropriate
 
• If the adverse event is determined by unanimous decision of the DLRM members to be related to study drug and clinically or medically significant, no further doses should be administered at this dose and no dose escalation should proceed. Enrollment of the study may continue at a lower dose or a lower dose cohort may be added to the study.
 
• Otherwise, upon unanimous decision of the DLRM members, one of the following decisions may be made: 
 
○ resume enrollment of the cohort as planned
 
○ resume enrollment of the cohort at a lower dose
 
○ expand the cohort at the same dose
 
○ add a lower dose cohort to the study
 
○ escalate to an intermediate dose (a dose lower than the next planned dose)
 
○ escalate to the next planned dose
 
 
 

Page 2 of 2

The Amgen Medical Monitor will be unblinded to treatment assignment throughout the duration of the study. For other DLRM members, a subject's treatment assignment should only be unblinded when knowledge of the treatment is essential for the further management of the subject, or may impact the safety of subjects currently enrolled, or subjects in subsequent cohorts.

### 6.3 Hepatotoxicity Stopping and Rechallenge Rules

Subjects with abnormal hepatic laboratory values (ie, alkaline phosphatase [ALP], aspartate aminotransferase [AST], alanine aminotransferase [ALT], total bilirubin [TBL]) and/or international normalized ratio [INR] and/or signs/symptoms of hepatitis (as described below) may meet the criteria for withholding or permanent discontinuation of Amgen investigational product or other protocol-required therapies as specified in the

FDA Guidance for Industry Drug-Induced Liver Injury: Premarketing Clinical Evaluation, July 2009.

### 6.3.1 Criteria for Permanent Withholding of Amgen Investigational Product and Other Protocol-required Therapies Due to Potential Hepatotoxicity

Following the single-dose administration of study drug, the subject should be followed according to the recommendations in [Appendix A](#) (Additional Safety Assessment Information) for possible drug-induced liver injury (DILI), if ALL of the criteria below are met:

- TBL > 2x upper limit of normal (ULN) or INR > 1.5
- AND increased AST or ALT from the relevant baseline value as specified below:

Baseline AST or ALT value	AST or ALT elevation
< ULN	≥ 3x ULN

- AND no other cause for the combination of the above laboratory abnormalities is immediately apparent; important alternative causes for elevated AST/ALT and/or TBL values include, but are not limited to:
  - Hepatobiliary tract disease
  - Viral hepatitis (eg, Hepatitis A/B/C/D/E, Epstein-Barr Virus, cytomegalovirus, Herpes Simplex Virus, Varicella, toxoplasmosis, and Parvovirus)
  - Right sided heart failure, hypotension or any cause of hypoxia to the liver causing ischemia.
  - Exposure to hepatotoxic agents/drugs or hepatotoxins, including herbal and dietary supplements, plants and mushrooms
  - Heritable disorders causing impaired glucuronidation (eg, Gilbert's Syndrome, Crigler-Najjar syndrome) and drugs that inhibit bilirubin glucuronidation (eg, indinavir, atazanavir)
  - Alpha-one antitrypsin deficiency
  - Alcoholic hepatitis
  - Autoimmune hepatitis
  - Wilson's disease and hemochromatosis
  - Nonalcoholic Fatty Liver Disease including Steatohepatitis (NASH)
  - Non-hepatic causes (eg, rhabdomyolysis, hemolysis)

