#### **4.2 Exclusion Criteria**

201 Currently receiving treatment in another investigational device or drug study, or less than 30 days or 5 half-lives (whichever is longer), since ending treatment on another investigational device or drug study(s) prior to receiving the first dose of investigational product

202 Women who are lactating/breastfeeding or who plan to breastfeed while on study through 90 days after receiving the dose of investigational product

203 Men with partners who are pregnant or planning to become pregnant while the subject is on study through 90 days after receiving the dose of investigational product

204 Positive pregnancy test at screening or day -1

205 Estimated glomerular filtration rate (eGFR) of less than 60 mL/min/1.73m^2 as calculated using the Chronic Kidney Disease Epidemiology Collaboration (CKD-EPI) equation at screening or day -1

206 Triglycerides ≥ 5.65 mmol/L (ie, 500 mg/dL) at screening

207 Gamma-glutamyltransferase (GGT) or ALP above the upper limit of normal (ULN) of the laboratory's reference range at screening or day -1. GGT or ALP may be retested once in case of an elevated GGT or ALP within 1.1 x ULN of the laboratory's reference range at screening or day -1.

208 ALT and AST > 1.1 upper limit of normal of the laboratory's reference range at screening or day -1

209 Prothrombin time or aPTT outside of the laboratory's normal reference range at screening or day -1

- 210 History of hyperthyroidism or hypothyroidism, unless treated and/or on stable therapy for > 6 months prior to enrollment, and confirmed by a thyroid stimulating hormone (TSH) level within the laboratory's normal reference range. Subjects with minor abnormalities in TSH may, at the principal investigator's discretion, be included if the subject is without clinical evidence of hyper- or hypothyroidism and additional thyroid function studies are within the laboratory's normal reference range.
- 211 History of malignancy of any type, other than in situ cervical cancer or surgically excised non-melanomatous skin cancers occurring more than 5 years prior to randomization
- 212 Positive results for human immunodeficiency virus (HIV) antibodies, hepatitis B surface antigen (HBsAg), hepatitis B core antibody (HBcAb), or hepatitis C virus ribonucleic acid (RNA). For hepatitis C, hepatitis C antibody (HepCAb) testing is done at screening, followed by hepatitis C virus RNA by polymerase chain reaction (PCR) if hepatitis C antibody is positive.

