#### **9.1.2 Serious Adverse Events**

A serious adverse event is defined as an adverse event that meets at least 1 of the following serious criteria:

- fatal
- life threatening (places the subject at immediate risk of death)
- requires in patient hospitalization or prolongation of existing hospitalization
- results in persistent or significant disability/incapacity

- congenital anomaly/birth defect
- other medically important serious event

An adverse event would meet the criterion of “requires hospitalization”, if the event necessitated an admission to a health care facility (eg, overnight stay).

If an investigator considers an event to be clinically important, but it does not meet any of the serious criteria, the event could be classified as a serious adverse event under the criterion of “other medically important serious event”. Examples of such events could include allergic bronchospasm, convulsions, blood dyscrasias, drug induced liver injury (DILI) (see [Appendix A](#) for DILI reporting criteria), or events that necessitate an emergency room visit, outpatient surgery, or urgent intervention.

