#### **10.1.3 Covariates and Subgroups**

Baseline values may be used as a covariate in analyses. For any variable, unless otherwise defined, baseline is defined as the last assessment taken prior to the first administration of AMG 529 or placebo.

No subgroup analyses are planned. Within each cohort, subjects will be randomized so that 6 subjects receive AMG 529 and 2 subjects receive placebo in each cohort. Data from placebo-treated healthy subjects will be pooled across the cohorts for analysis.

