**14. APPENDICES**

## **Appendix A. Additional Safety Assessment Information**

### **Drug-induced Liver Injury Reporting & Additional Assessments**

#### **Reporting**

To facilitate appropriate monitoring for signals of DILI, cases of concurrent AST or ALT and TBL and/or INR elevation according to the criteria specified in [Section 6.3](#) require the following:

- The event is to be reported to Amgen as a serious adverse event within 24 hours of discovery or notification of the event (ie, before additional etiologic investigations have been concluded)
- The appropriate CRF (eg, Event CRF) that captures information necessary to facilitate the evaluation of treatment-emergent liver abnormalities is to be completed and sent to the Amgen.

Other events of hepatotoxicity and potential DILI are to be reported as serious adverse events if they meet the criteria for a serious adverse event defined in [Section 9.2.1.2](#).

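### Exclusion 208 joins ALT and AST with 'and' where 'or' appears intended; and, if no table row was lost, Section 6.3.1 gives no threshold when both enzymes start at or above the ULN

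*Protocol*

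**What the plan says.** **Entry.** Protocol 4.2, exclusion 208, opens "ALT and AST > 1.1 upper limit of normal of the" local laboratory range, applied at screening or day -1. The criteria on either side name two analytes each and join them with 'or': 207 (GGT or ALP above the ULN) and 209 (prothrombin time or aPTT outside the normal range). Inclusion 101 and exclusion 213 leave room to refuse a subject on the investigator's judgement.

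**After dosing.** Protocol 6.3.1 sets three criteria for possible drug-induced liver injury, all of which must be met:

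- bilirubin above 2 x ULN or INR above 1.5;
- "AND increased AST or ALT from the relevant baseline value as specified below";
- "AND no other cause for the combination of the above laboratory abnormalities is immediately apparent".

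The table attached to the second criterion has, in the extracted text, a single row: baseline below the ULN, rise to at least 3 x ULN.

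**Reporting.** Appendix A takes "cases of concurrent AST or ALT and TBL and/or INR elevation according to the criteria specified in" Section 6.3 and requires of them: "The event is to be reported to Amgen as a serious adverse event within 24 hours of discovery or notification of the event". For everything else it adds: "Other events of hepatotoxicity and potential DILI are to be reported as serious adverse events if they meet the criteria" for seriousness. Its close-observation rule is separate. It applies to any AST or ALT above 3 x ULN, or to a doubling from a raised pre-drug value.

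**Baseline.** Protocol 10.1.3 says that, unless otherwise defined, "baseline is defined as the last assessment taken prior to the first administration of AMG 529 or placebo".

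**The concern.** This is a first-in-human study of an antibody whose target receptor sits mainly on liver cells. Section 2.3 expects ALP, and possibly GGT, to rise through the drug's pharmacology, and expects the other liver tests, ALT and AST among them, to show no clinically relevant increase. That contrast is easiest to read when both enzymes are close to normal at entry, which is what 208 appears meant to secure. With 'and', the rule does not secure it. GGT slightly above the ULN on retest excludes a subject under 207, while ALT at 2.5 x ULN with a normal AST does not exclude under 208.

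The second matter is one of coverage. 208 tolerates values up to 1.1 x ULN on any reading, but the 6.3.1 table as extracted stops below 1.0. Two subjects with the same post-dose results could then be classified differently because their baselines differ slightly, and only one would come under the automatic report.

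**Working it through.** The plan gives no figure on this point, so the check applies the rules as written. Values are multiples of the ULN, shown as ALT/AST.

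**Step 1: exclusion 208.**

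- With 'and': excluded if ALT > 1.1 and AST > 1.1.
- With 'or': excluded if ALT > 1.1 or AST > 1.1.

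**Step 2: which baseline 6.3.1 uses.** Section 6.3.1 defines none of its own, so I take the definition in 10.1.3. In the schedules (Tables 4 and 5), chemistry is drawn at screening and day -1 and then not until 24 hours after dosing. The baseline is therefore the day -1 value, one of the two that 208 tests.

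**Step 3: the 6.3.1 rule.** Met = (bilirubin > 2 or INR > 1.5) and no other apparent cause and E, where E is the enzyme criterion. The table headings do not say whether the same enzyme must fill both columns, so I test both readings:

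- same enzyme: (baseline ALT < 1 and later ALT ≥ 3) or (baseline AST < 1 and later AST ≥ 3);
- either enzyme: the lower baseline < 1 and the higher later value ≥ 3.

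**Step 4: cases.** For illustration, the post-dose values are 5/4 with bilirubin 2.5 and no other apparent cause.

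| Day -1 ALT/AST | 208 with 'and' | 208 with 'or' | 6.3.1 met (both readings) |
|---|---|---|---|
| 0.9/0.9 | admitted | admitted | yes |
| 2.5/0.9 | admitted | excluded | yes |
| 2.5/1.05 | admitted | excluded | no |
| 1.00/1.00 | admitted | admitted | no |
| 1.05/1.05 | admitted | admitted | no |
| 1.10/1.10 | admitted | admitted | no |

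'Admitted' means not excluded by 208; 101 and 213 could still exclude. The Appendix A close-observation trigger (above 3 x ULN) is met in every row.

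**Step 5: what the cases show.** The two matters are separate. Changing 208 to 'or' removes 2.5/0.9 and 2.5/1.05 but leaves the 1.0 to 1.1 band eligible with no row in the table. Adding a row does not stop 2.5/0.9 from entering. When both baselines are at or above 1, E is false under either reading, so the gap does not depend on how the columns are read.

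**Step 6: would 3 x ULN still mark a real rise?** With 208 corrected, the highest admitted baseline is 1.1, so 3 x ULN is at least a 3/1.1 = 2.73-fold rise. With 208 uncorrected and a baseline of 2.5, it would be only 3/2.5 = 1.2-fold. For baselines of 1.0 to 1.1, the doubling rule for close observation starts at 2.0 to 2.2 x ULN, so it remains the earlier tier.

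**The case against.** **On 208.** 'ALT and AST above 1.1' can be read as 'each of these', and an investigator recruiting healthy volunteers would probably refuse ALT at 2.5 x ULN under 101 or 213. Both remarks are fair. A reader might infer that the sponsor meant to admit subjects with one raised enzyme, or that such subjects will in practice be enrolled. The documents support neither, and 207 and 209 suggest the opposite intent. What stands is that a fixed eligibility limit should not depend on a generous reading or on discretion.

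**On 6.3.1.** The missing row may be a product of PDF extraction. A table keyed to baseline, together with Appendix A's provision for raised pre-drug values, is what one would expect to see if a second row had been lost. The extracted text cannot settle this. In addition, Appendix A points to Section 6.3 as a whole, and that section refers to an FDA guidance that is not among the documents.

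**On consequence.** A reader might infer that a serious liver event would go unmonitored or unreported. It would not, on these documents. Close observation applies above 3 x ULN whatever the baseline. Section 9.1.2 lists drug-induced liver injury among its examples and says that "the event could be classified as a serious adverse event under the criterion of" other medically important events, and Section 9.2.1.2 requires every serious adverse event to be submitted within 24 hours. The unblinded medical monitor may suspend dosing, and the Grade 3 rule in Table 3 still operates. Dosing is single, so no later dose to that subject is at stake. What changes is that classification becomes a matter of judgement instead of following from the rule.

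A reader might also extend the gap to any subject with one raised enzyme. The table headings do not say whether the same enzyme must fill both columns, so no gap is claimed there.

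**Conclusion.** Exclusion 208 is worded so that, taken literally, it excludes only subjects with both enzymes above 1.1 x ULN. This is the firm part: it is running text and depends on no table. That 'or' was intended is an inference from the rule's purpose and from 207 and 209.

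The 6.3.1 gap is conditional. It exists only if the original table has no further row, and only for subjects with both enzymes at or above the ULN on day -1, taking baseline as defined in 10.1.3. Its effect is confined to the automatic liver-injury classification and the report tied to it.

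Severity is minor. Few subjects are likely to be affected, and the documents give no basis for a number.

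**What to change.** 1. In exclusion 208, write ALT or AST > 1.1 x ULN. This is a one-word change, with the multiplication sign supplied.
2. Check the 6.3.1 table in the original PDF. If there is no further row, state that the enzyme criterion is ≥ 3 x ULN regardless of baseline. A separate row for baselines at or above the ULN would also close the gap, with its threshold set by the clinical team.
3. Leave the Appendix A close-observation trigger as it is.

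Make the change in 208 whatever the table check shows. Neither edit affects sample size, visit schedule or analysis.
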